#### 476 **8.4. Sensitivity Analyses**

477 Confounding

A sensitivity analysis for the primary outcome, HbA1c, will also be conducted if potential confounding
factors collected at baseline are detected.

- The imbalance will be assessed based on clinical judgment reviewing the distributions in the two
  treatment arms, not on a p-value. The person making this judgement will be unaware of whether there is
  an association between baseline variables and study outcome.
- 483
- 484 Missing Data
- 485 Missing data will be handled using direct likelihood method for the primary analysis. It is worth noting 486 that all statistical methods for handling missing data rely on untestable assumptions and there is no one 487 correct way to handle missing data. Our goal is to minimize the amount of missing data so that the 488 results will not be sensitive to which statistical method is used.
- To that end, sensitivity analyses will be performed to explore whether results are similar for primaryanalysis when using different methods. The following methods will be applied:
  - Rubin's multiple imputation with treatment group in the imputation model
  - Available cases only
- Multiple imputation with pattern mixture model assuming the dropout trajectory of the AID group was that of the Control group (Mallinckrodt and Clark, 2003)
- Tipping point analysis to determine the magnitude of selective dropout bias necessary to alter conclusions of the study.
- 497

491

492

#### 498 8.5. Secondary Binary HbA1c and CGM Metrics

- For the binary HbA1c outcomes, risk-adjusted percentages by treatment group will be computed at 13 weeks from a logistic regression model. The logistic regression will adjust for baseline HbA1c (as a continuous factor) and clinical site using generalized estimating equations (GEE).
- 502 Similar analyses will be done for the binary CGM outcomes.
- 503

#### 504 8.6. Insulin, Weight, Blood Pressure, and Lipids Analyses

- For insulin, weight, BMI, blood pressure, lipid, and creatinine metrics, summaries and comparisons will
   be made using similar statistics and linear models as described above for the primary HbA1c analysis.
- 507 For insulin metrics, formal analyses will be done comparing the 13-week metrics between the two
- 508 groups while adjusting for baseline. In addition to these, tabulations and plots will be done with insulin
- 509 metrics at baseline, 1, 8, and 13 weeks. Additionally, the post-randomization insulin data in the AID

510 group will be differentiated by manual or automatic mode of delivery – in terms of events and amount of 511 insulin.

512

#### 513 8.7. Questionnaires/PRO

For each questionnaire, summary statistics (mean  $\pm$  SD and n(%)) will be given for each item and at each time point when the questionnaire was administered. For questionnaires with a scoring guide available that are administered at both at the baseline and at 13 weeks and for all total scores and subscales thus calculated, the two arms will be compared using a linear model similar to the one described above for the primary outcome. All questionnaires' results will be tabulated, but formal tests will be done only for questionnaires with baseline and 13-week results and done in both arms.

520

#### 521 9. Safety Analyses

522

All enrolled participants will be included in the safety analyses and all of their post-randomization safety
events will be reported by the treatment group. Separately, any adverse events occurring between
screening and randomization will be reported.

All reportable adverse events will be tabulated by the treatment group. Details will be provided in a
listing of each event, including Medical Dictionary for Regulatory Activities (MedDRA) term and
MedDRA System Organ Class. Safety analyses for the RCT will include events occurring on or after
randomization until and including the 13-week visit or Day 98 from randomization, whichever occurs
first.

- 531 The safety metrics will include:
  - Severe hypoglycemia
- Diabetic ketoacidosis
- Hyperosmolar hyperglycemic syndrome
- Other serious adverse events
- Unanticipated adverse device effects
- Hypoglycemia and prolonged hyperglycemia endpoints listed as effectiveness endpoints
- Infusion set failures
- Other device malfunctions/device issues
- 540

- All safety metrics listed above will be tabulated by the treatment group. Formal statistical testing only will be performed for selected safety endpoints. For the following outcomes, mean  $\pm$  SD or summary statistics appropriate to the distribution will be tabulated by treatment group and formal statistical comparisons will be performed if there are enough events (at least 5 events combined between the two treatment groups):
- Number of SH events and SH event rate per 100 person-years
- Number of DKA events and DKA event rate per 100 person-years

- Number of hyperosmolar hyperglycemic syndrome events and rate per 100 person-years
  - Other serious adverse events

If enough events occur for the severe hypoglycemia and DKA outcomes and other serious adverse
events, the numbers of events will be compared between the two treatment groups during the RCT using
a robust Poisson regression as detailed in the SAP.

553

549

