	This equates with a maximum of 220 using the AID system for 13 weeks and 110 using pre-study basal-bolus insulin delivery method plus the study CGM. Assuming 10% drop out rate in each group, there will be 200 using the system for 13 weeks.
	Approximate Study Goals
	- Minimum 25% MDI users
	- Minimum 30% of a minority race or ethnicity
	- Minimum 10% older than 50 years old
	- Minimum 20% using an SGLT2 inhibitor,20% using a GLP-1 receptor agonist, and a minimum of 10% using both
	Minimum of 15% with TDI> 100 units/day and attempt to enrich cohort with participants with TDI >200 units

PARTICIPANT AREA	DESCRIPTION
	 Minimum of 25% using a form of fixed dosing to calculate meal boluses (e.g., fixed dose at meal or fixed dose for small/medium/large meal [i.e., dose not determined by carbohydrate counting]) Maximum of 60% with HbA1c <8% (based on screening HbA1c or HbA1c available within the last 30 days) and maximum of 10% with screening HbA1c <7%
Treatment Groups	Random assignment 2:1 to an intervention group or control group:
	 Intervention group: t:slim X2 insulin pump with Control-IQ technology and Dexcom G6 CGM
	Control group: Continuation of pre-study basal-bolus insulin delivery method, plus use of study CGM (Dexcom G6)
Participant Duration	~13-17 weeks, depending on duration of run-in phase
Study Duration (planned)	~9 months from first enrollment until last participant visit (assuming 4-month recruitment period; study duration will be extended as needed to complete recruitment)
Protocol Overview/Synopsis	Screening Visit
	• Informed consent obtained and participant screened for eligibility. Testing for eligibility assessment and baseline will include:
	 Medical history, including total daily insulin dose, prior severe hypoglycemia, diabetic ketoacidosis (DKA), hyperosmolar hyperglycemic syndrome (HHS), and hospitalizations for these events.
	 HbA1c with point-of-care device or local lab, unless available from the prior 30 days
	 Focused physical exam, including height and weight to compute body mass index (BMI) and blood pressure
	 Urine pregnancy test for participants capable of becoming pregnant
	o EKG unless performed within 12 months prior to screening
	 Subjective Numeracy Scale Patient-reported outcome (PRO) surveys (see section 8.3), including frequency of non-severe hypoglycemia during the prior 3 months
	CGM Run-in
	Eligible participants will be started on the study CGM, if applicable

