- Device malfunctions will be handled by the Sponsor or designee as described below. In the case
- of a CGM transmitter or sensor device malfunction, information will be forwarded to Dexcom by
- the site personnel, to be handled by their complaint management system.

1176

1140

1141

- Where an adverse event is suspected to be related only to the study provided insulin from Novo
- Nordisk, and does not result from a possible interaction with the investigational medical device,
- the investigator or the sponsor are encouraged to report the case to the FDA or competent
- authority. Where made aware of such case, the competent authority should apply the guidance
- provided in the Good Pharmacovigilance Practices Module VI with regard to the management of
- this type of safety report. While reporting the suspected adverse reaction, the relevant
- information regarding the CT (i.e. clinical trial number) or Study ID number must be included in
- the report.

1185 **9.5 Safety Oversight**

- The study Medical Monitor will review all adverse events and adverse device events that are
- reported during the study. SAEs typically will be reviewed within twenty-four (24) hours of
- reporting. Other AEs typically will be reviewed on a weekly basis.
- The Sponsor and Clinical Study Director will be informed of all cases of severe hypoglycemia
- and DKA or HSS and the Medical Monitor's assessment of relationship to the study device; and
- informed of all reported device issues. A Data and Safety Monitoring Board (DSMB) will
- provide safety oversight. The DSMB will be informed of all cases of severe hypoglycemia,
- DKA, and HHS irrespective of device relationship, all device-related SAEs, and all UADEs at
- the time that they occur during the study and will review compiled safety data at periodic
- intervals. The DSMB also will be informed of any ADEs not meeting criteria for a UADE if the
- 1196 Medical Monitor requests the DSMB review. The DSMB can request modifications to the study
- protocol or suspension or outright stoppage of the study if deemed necessary based on the
- totality of safety data available. Details regarding the DSMB's role will be documented in a
- separate DSMB charter.

1200

1201

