294 295 296 297	For security and confidentiality purposes, participants will be assigned an identifier that will be used instead of their name. Protected health information gathered for this study will be shared with the coordinating center, the Jaeb Center for Health Research in Tampa, FL. De-identified participant information may also be provided to research sites involved in the study.

1298	Chapter 11: Statistical Considerations
1299	11.1 Statistical and Analytical Plans
1300 1301	The approach to sample size and statistical analyses are summarized below. A detailed Statistical Analysis Plan will be written and finalized prior to the completion of the study.
1302 1303 1304	The primary statistical analyses will involve comparisons of the randomized treatment groups. Additionally, certain single-arm analyses will be conducted on the data collected for the AID group as described in section 11.15.
1305	11.2 Statistical Hypotheses
1306 1307 1308	The primary endpoint for this study is HbA1c at 13-weeks adjusted for baseline HbA1c. The intervention will be considered effective if the AID group is superior to the Control group using a statistical significance of α =0.05.
1309	The null/alternative hypotheses for the primary endpoint are:
1310 1311 1312	 Null Hypothesis: There is no difference in mean HbA1c at 13 weeks between AID and Control Alternative Hypothesis: Mean HbA1c at 13 weeks is different for AID and Control.
1313 1314	Similarly, the null and alternative hypotheses for all of the secondary efficacy endpoints in the hierarchy are:
1315 1316 1317	 Null Hypothesis: There is no difference in the endpoint at 13 weeks between AID and Control Alternative Hypothesis: Endpoint at 13 weeks is different for AID and Control.
1318	11.3 Sample Size
1319 1320 1321 1322	The sample size of 330 randomized participants was selected to provide sufficient exposure to the AID system for regulatory purposes. This equates with a maximum of 220 using the AID system for 13 weeks. Assuming 10% drop out rate in each group, there will be 200 using the system for 13 weeks.

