1481 1482 1483	All randomized participants will be included in the safety analyses and all of their post-randomization safety events will be reported. Separately, any adverse events occurring between screening and randomization will be reported.
1484 1485 1486 1487 1488	All reportable adverse events will be tabulated by treatment group. Details will be provided in a listing of each event, including Medical Dictionary for Regulatory Activities (MedDRA) term and MedDRA System Organ Class. Safety analyses for the RCT will include events occurring on or after randomization until and including the 13-week visit or Day 98 from randomization, whichever occurs first.
1489 1490 1491 1492	Formal statistical testing only will be performed for selected safety endpoints. For the following outcomes, mean \pm SD or summary statistics appropriate to the distribution will be tabulated by treatment group and formal statistical comparisons will be performed if there are enough events (at least 5 events combined between the two treatment groups):
1493 1494 1495 1496	 Number of SH events and SH event rate per 100 person-years Number of DKA events and DKA event rate per 100 person-years Number of hyperosmolar hyperglycemic syndrome events and rate per 100 person-years Other serious adverse events
1497 1498 1499	If enough events occur for the severe hypoglycemia and DKA outcomes and other serious adverse events, the numbers of events will be compared between the two treatment groups during the RCT using a robust Poisson regression as detailed in the SAP.
1500	11.9.1 Safety Tabulations Specific to the AID Group
1501	For the AID Group, all of the following will be tabulated:
1502 1503 1504	 Adverse device effects (ADE) Serious adverse device events (SADE) Unanticipated adverse device effects (UADE)
1505	11.10 Additional Tabulations and Analyses
1506	The following tabulations will be performed according to treatment group:
1507 1508 1509 1510 1511 1512 1513	 Baseline demographics and clinical characteristics A flow chart accounting for all participants for all visits Visit completion rates for each follow-up visit Protocol deviations Modifications in non-insulin diabetes drugs during the study Number and reasons for unscheduled visits and phone calls Amount of CGM data during the 13 weeks of the study
1514	11.11 Planned Interim Analyses

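### SAP 9 starts safety tests at 5 combined events with no named test statistic and no rule for a zero-event arm; under the usual sandwich Wald reading, 5 to 8 AID events against 0 gives p near 0

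*SAP*

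**What the plan says.** Protocol 11.1 promises that "A detailed Statistical Analysis Plan will be written and finalized prior to the completion of the study". Protocol 11.9 then says that event numbers will be "compared between the two treatment groups during the RCT using a robust Poisson regression as detailed in the SAP". In the Protocol that pointer works. SAP 9 carries the same sentence over, "a robust Poisson regression as detailed in the SAP", so the SAP points to itself. SAP 6.1 adds only that p-values are two-sided; its nonparametric and M-estimation fallback is for skewed primary and secondary outcomes.

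Formal comparison starts at "at least 5 events combined between the two" arms, with no minimum per arm. Allocation is unequal: "Random assignment 2:1 to an intervention group or control group" (Protocol Summary, Treatment Groups).

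The outcomes listed for formal comparison include "Number of hyperosmolar hyperglycemic syndrome events and rate per 100 person-years". The method sentence opens "If enough events occur for the severe hypoglycemia and DKA outcomes and other serious adverse" events and does not name HHS.

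**The concern.** A low trigger, no minimum per arm and 2:1 allocation together make an empty Control arm a foreseeable result, and Poisson regression has no finite rate ratio there. A sandwich Wald test does not fail visibly in that case. It returns an extremely small p-value, which for severe hypoglycemia or DKA would read as strong evidence of harm from the device when an exact test on the same counts is not significant. Because the statistic is unnamed, the choice among tests that disagree could also be made after the split is known. HHS is marked for formal comparison but has no stated method.

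**Working it through.** **Inputs.** Arms of 220 and 110 (SAP 1, Sample Size); trigger of 5 combined events (SAP 9); two-sided p (SAP 6.1). The plan gives no error rate, power or expected event rate for the safety tests, so there is no stated figure to reproduce.

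**Assumptions made here.** Equal follow-up per participant, one event per participant unless stated, no covariates, level 0.05, and robust taken to mean a sandwich variance with a Wald test. Splits are written AID-Control.

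**1. Chance of an empty Control arm with equal rates.** Given K events this is (2/3)^K: 13.2%, 8.8%, 5.9% and 3.9% for K = 5, 6, 7, 8. An empty AID arm has chance (1/3)^K, or 0.4% at K = 5.

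**2. Sandwich Wald with events in both arms.** With a AID and c Control events, log RR = log(a/220) − log(c/110) and variance = 1/a − 1/220 + 1/c − 1/110. At 4-1: log RR = 0.693, variance = 0.2500 − 0.0045 + 1 − 0.0091 = 1.236, SE 1.112, p = 0.53. The test behaves normally.

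**3. Sandwich Wald at 5-0.** The fitted log RR runs away: 11.1, 21.1 and 30.1 at iteration limits of 10, 20 and 30. The robust SE does not grow with it. The AID part is 1/5 − 1/220 = 0.1955. The Control part is 110μ²/(110μ)² = 1/110 = 0.0091, where it ought to be infinite. So the SE lies between √0.1955 = 0.44 and √0.2045 = 0.45, and p is below 1e-100.

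**4. Exact conditional test.** Given K, the AID count is Binomial(K, 2/3). At 5-0, add the splits no more likely than the observed one: 32/243 (5-0) + 10/243 (1-4) + 1/243 (0-5) = 43/243 = 0.177.

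| Split | Sandwich Wald p | Exact p |
|---|---|---|
| 5-0 | near 0 | 0.18 |
| 6-0 | near 0 | 0.19 |
| 7-0 | near 0 | 0.10 |
| 8-0 | near 0 | 0.06 |
| 9-0 | near 0 | 0.034 |
| 10-1 | 0.12 | 0.11 |

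From 9-0 the exact test also rejects. (Doubling the tail instead gives 0.052 at 9-0 and 0.035 at 10-0.) At 10-1 the exact evidence is stronger than at 5-0, yet the Wald test rejects only 5-0.

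**5. Other tests at 5-0.** Robust score 0.025, likelihood ratio 0.044, model-based score 0.114, model-based Wald 0.999. The robust score p becomes 0.059 if one participant has two of the five events and 0.32 if one has all five. The sandwich Wald p is still about 3e-99 in that last case.

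**6. Error over the whole rule.** Let K be Poisson, test only if K ≥ 5, and sum the binomial probabilities of splits with Wald p<0.05. Total two-sided error under no difference:

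| Expected events | 2 | 5 | 7 | 10 | 12 | 20 |
|---|---|---|---|---|---|---|
| Error | 0.7% | 5.4% | 6.4% | 5.3% | 4.4% | 4.1% |

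At 7 expected events, 4.8 of the 6.4 points are in the harm direction. Conditional on exactly 5, 6 or 7 events the error is 13.6%, 10.6% and 6.5%.

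**The case against.** The strongest reply is that the SAP never names a Wald test. At 5-0, the model-based score, model-based Wald and exact tests all stay above 0.05. The robust score test rejects at 5-0 only with one event per participant, and repeat events are a common reason for choosing a robust variance. This stands: the near-zero p belongs to the usual reading of the method, not to everything the wording allows.

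The plan is also not silent. The word robust points to a variance estimator, and SH, DKA and HHS are to be given as rates per 100 person-years, which implies person-time. What is missing is narrower: the test statistic, an explicit offset and a zero-arm rule.

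The practical reach is limited. Protocol 11.11 and SAP 14 plan no formal stopping rule that uses these p-values, and SAP 9 tabulates and lists all reportable events by arm, so a reader would see 5 versus 0 beside the p. Protocol 9.5 adds: "The DSMB will be informed of all cases of severe hypoglycemia", as well as DKA and HHS.

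A reader might infer that any empty Control arm yields a false harm signal, or that the 13.6% is the error of the plan's rule. The documents support neither. From 9-0 the exact test rejects too, and 13.6% applies only given exactly 5 events. Nor do they show that the trial will fall in the affected range, since no event rates are given.

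**Conclusion.** Wrong as written, low severity. SAP 9 leaves its safety test undefined by pointing to itself. Under the sandwich Wald reading, the stated trigger permits a p near 0 for 5 to 8 AID events against 0, where exact p runs from 0.06 to 0.19. From 9-0 only the size of p is wrong. Over the whole rule the two-sided error is at most 6.4%, near 7 expected events, and is below 5% by 12. The sizes rest on the assumptions listed in the check. The self-reference, the absent zero-arm rule and the omission of HHS rest on the text alone. What is at stake is a misleading reported p-value for key safety endpoints, not a trial decision.

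**What to change.** In SAP 9, replace the self-reference with a named rule covering SH, DKA, HHS and other SAEs:

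- When total events are below a cut-off fixed in advance (for example 20), or either arm has none, use the exact conditional Poisson (binomial) test with person-time. Report the exact confidence interval for the rate ratio. At 5-0 the lower 97.5% bound is q/(1−q)/2 with q = 0.025^(1/5) = 0.478, which gives 0.46; there is no upper bound.
- State the two-sided convention, since the p-value at 9-0 depends on it (0.034 or 0.052).
- If events repeat within participants, take the p-value from a participant-level permutation test.
- Otherwise use Poisson regression with a log person-time offset and a sandwich-variance Wald test.
- State that a non-significant result is not evidence of safety.

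The work is SAP wording and a few lines of code. The downside should be stated: all-AID splits of 5 to 8 events can no longer reach p<0.05. If the AID rate is three times Control, power to flag harm with the exact test throughout, against sandwich Wald, is:

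| Expected total events | 3.5 | 7 | 14 | 21 |
|---|---|---|---|---|
| Sandwich Wald | 11% | 26% | 22% | 39% |
| Exact throughout | 0.2% | 6% | 28% | 45% |

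Total null error with the exact test throughout stays below 4% at the values checked, from 2 to 20 expected events. With the cut-off at 20, the same enumeration gives the same power to the nearest percent and a null error of 4.3% at 20 expected events. The power lost at low counts comes from the 5-0 to 8-0 splits, the same ones that produce the false signals.

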#### 554 **10. Device Issues**

555

All enrolled participants will be included, and all of their post-randomization reported device issues will
 be reported by the treatment group. Separately, any device issues occurring between screening and
 randomization will be reported.

- 559 The following tabulations and analyses will be performed to assess device issues:
- Device malfunctions requiring study team contact and other reported device issues.
- Rate of different failure events and alarms per 24 hours recorded by the Control-IQ system overall and by study month.
- 563 564

565 566

570

571

572 573

574

575

# **11. Protocol Adherence and Retention**

The following measures of adherence will be tabulated overall pre-randomization and by treatmentgroup post-randomization:

- Number of protocol and procedural deviations.
  - Flow chart accounting for all enrolled participants up to end of the study.
  - Flow chart of all scheduled visits and phone contacts.
  - Number of and reasons for unscheduled visits and phone calls.
  - Number of participants who stopped CGM or AID treatment.
  - Modifications in non-insulin diabetes drugs during the study
  - Amount of CGM data during the 13 weeks of the study
- 576 577

# 12. Intervention Adherence

578 579

582

584

585

586

